**Aim 1b: To assess whether targeting MAP to a level above an individual's lower CBF autoregulatory threshold during CPB reduces the frequency of cognitive decline 1 year after surgery compared with the use of standard blood pressure management.** In Aim 1, we will test whether the Intervention and Control groups have the same risk of the primary composite neurologic endpoint of stroke, DWI lesion, or cognitive decline 4 to 6 weeks after surgery (i.e., null hypothesis). This will be done using a two-sided test of proportions at 5% significance level. We will first calculate and report the relative risk (RR) of composite neurologic outcome by comparing the Intervention and Control groups without adjusting for any potential confounders (i.e., the unadjusted RR). In addition, we will construct an adjusted estimate of RR using a generalized linear model (GLM) with Poisson distribution and robust standard errors. The candidate models will include study group as the primary independent variable as well as extra- or intracranial arterial stenosis determined by MRA, patient age, gender, and baseline risk factors that are assumed to be highly predictive of the outcome, such as history of hypertension, diabetes, or prior stroke. To assess potential effect modification by cerebral arterial stenosis, age, gender, hypertension, diabetes, or prior stroke (Aim 1a), we will calculate the unadjusted RR stratified by these variables. We will use a test of homogeneity to compare stratum-specific estimates of RR. Finally, we will use the model developed in Aim 1 to report stratum-specific adjusted estimates of RR by introducing appropriate interaction terms of these variables and study group in the GLM model. We will compute the Z-score for the cognitive tests to normalize the distribution to the control data. The individual Z-scores will be combined into an average score and re-normalized. To assess postoperative change in cognitive function for up to 1 year (Aim 1b), we will use population-average marginal models estimated using generalized estimating equations (GEE) with exchangeable working correlation structure. The model will include assessment time with 2 indicator variables for 1 year and 4 to 6 weeks postoperation and baseline as the reference group as well as Intervention Group, and their interaction to test whether postoperative trajectory of cognitive function differs by group.

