Our current enrollment trajectory suggests that at least 277 patients will have undergone the protocol of our study before the end of the funding period for the initial grant. At that point we would expect to have 101 patients who have undergone MRI for evaluation of DWI lesions. An additional 143 patients with complete MRI, stroke, and cognitive endpoint data are needed to reach the target of 244 patients with the primary, complete endpoint data. To reach this target, we will need to enroll an additional 350 patients in this renewal. Our recruitment projections for our initial funded study are a conservative estimate, as we have enrolled 277 patients to our study (101 have MRI data). On average, 5 to 8 patients are enrolled per month. These projections confirm that the plan for this submission of studying 350 additional patients (a total of 630 patients) will ensure completion of the study with 244 patients having all study assessments, including MRI, at the completion of the proposed study funding period.

In addition, we calculated the minimal sample size required to detect 0.2 SD difference in combined Z-score for cognitive tests normalized to the control group's data between the Intervention and Control groups with 80% power . We assume 2 follow-up points (4 to 6 weeks and 1 year after surgery) and an average within-patient correlation of 0.7 (observed in our preliminary data). The calculations indicate that we will need 177 observations per group, or 354 patients in total, to detect 0.2 SD difference with 80% power (assuming 5% Type I error). The study (first and second funding periods) will recruit a total of 489 patients to meet the MRI endpoint. Therefore, we will meet our goal of having 354 patients to detect the expected 0.2 SD difference in combined cognitive score seven with a 1-year drop-out rates high as 27%. Historically, the drop-out rate for cognitive testing at 1 year in similar populations has been between 3% and 24% .

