As of June 2016, we have enrolled 280 patients in the first five years and 244 patients in the second five year study. We need approximately 150 patients to complete enrollment.

In addition, we calculated the minimal sample size required to detect 0.2 SD difference in combined Z-score for cognitive tests normalized to the control group's data between the Intervention and Control groups with 80% power. We assume 2 follow-up points (4 to 6 weeks and 1 year after surgery) and an average within-patient correlation of 0.7 (observed in our preliminary data). The calculations indicate that we will need 177 observations per group, or 354 patients in total, to detect 0.2 SD difference with 80% power (assuming 5% Type I error). The study (first and second funding periods) will recruit a total of 489 patients to meet the MRI endpoint. Therefore, we will meet our goal of having 354 patients to detect the expected 0.2 SD difference in combined cognitive scores even with a 1-year drop-out rate as high as 27%. Historically, the drop-out rate for cognitive testing at 1 year in similar populations has been between 3% and 24%.

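### The Aim 1b cognitive model leaves the arms free to differ at baseline, so a valid test gives up precision that adjusting for baseline would recover

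*Combined protocol and SAP*

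**What the plan says.** The Aim 1b text in Study Statistics specifies "generalized estimating equations (GEE) with exchangeable working correlation structure". The model contains "assessment time with 2 indicator variables for 1 year and 4 to 6 weeks postoperation and baseline as the reference group". It also has a main effect for study group and group-by-time terms, and the latter are what is tested. Baseline is therefore an outcome row, and the group main effect is a freely estimated difference between arms at baseline.

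The sample-size text (after the Rapid Dissemination section, given twice) sets 177 per group "to detect 0.2 SD difference with 80% power (assuming 5% Type I error"), with two follow-up points and "an average within-patient correlation of 0.7".

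On timing, the Neurocognitive Function paragraph places the first test in the two weeks before surgery, and Patient Randomization places allocation after anaesthesia induction. The Missing data section adds random-effects and pattern-mixture models. The Statistical Analysis Plan section defines change from baseline in a Z-score scaled to the baseline SD. None of these adjusts the cognitive score for its baseline value or gives the arms a common baseline mean.

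**The concern.** With complete data, each group-by-time coefficient in this model equals the difference between arms in mean change from baseline. Randomisation follows the baseline test, so the group main effect estimates a quantity known to be zero. Estimating it subtracts the whole chance imbalance at baseline from each follow-up difference, when only the part predicted by the correlation should be removed.

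What is at stake is precision on the cognitive trajectory, including the 1-year time point that Aim 1b names. The information that would recover it is already collected.

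**Working it through.** **Inputs.** From the sample-size text: difference 0.2 SD, correlation ρ = 0.7, two follow-ups, 80% power, 5% type I error, 177 per group. Sidedness is not stated there; two-sided is assumed. Also assumed: the same correlation between every pair of visits, and equal SDs of 1.

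**Variance factors f** (variance of the arm difference = 2f/n):
- Change, two-visit mean: (1+ρ)/2 + 1 − 2ρ = 0.85 + 1 − 1.4 = 0.45
- Adjusted, two-visit mean: (1+ρ)/2 − ρ² = 0.85 − 0.49 = 0.36
- Change, 1 year: 2(1−ρ) = 0.60
- Adjusted, 1 year: 1 − ρ² = 0.51

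**The plan's own figure.** n = 2(1.96 + 0.842)² f/0.2². With f = 0.45 this is 2 × 7.85 × 0.45/0.04 = 176.6, so 177, exactly as stated. Follow-up scores alone (f = 0.85) would need 334. The plan was therefore sized on unadjusted change averaged over two visits.

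**Effect of adjustment**, with power = Φ(0.2/√(2f/177) − 1.96):

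| Contrast | f | Variance | SE at 177 per group | Power at 177 | n per group for 80% |
|---|---|---|---|---|---|
| 1 year | 0.60 → 0.51 | −15% | 0.0823 → 0.0759 (−8%) | 68% → 75% | 236 → 201 |
| Two-visit mean | 0.45 → 0.36 | −20% | 0.0713 → 0.0638 (−11%) | 80% → 88% | 177 → 142 |

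Inverting the information matrix of the planned model, with and without the group term, gives the same standard errors. A simulation of 20,000 trials gives variance reductions of 15.9% and 20.3%. A short run of 300 fitted GEEs gave 6.8% and 12.9%: the same direction, but too few replicates to set against exact algebra.

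**Joint 2-df interaction test at 177 per group.** The covariance of the two contrasts is (2/177) times a matrix with 0.60 on and 0.30 off the diagonal (change), or 0.51 and 0.21 (adjusted).
- Effect 0.2 at both visits: noncentrality (0.04 × 177/2) × 2/0.90 = 7.87, against × 2/0.72 = 9.83. Power 71% → 81%.
- Effect 0.2 at one visit only: 3.54 × 0.60/0.27 = 7.87, against 3.54 × 0.51/0.216 = 8.36. Power 71% → 74%.

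**Sensitivity.** Variance reduction by correlation (1 year / two-visit mean): 0.5, 25%/33%; 0.6, 20%/27%; 0.7, 15%/20%; 0.8, 10%/13%; 0.9, 5%/7%.

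The documents give no follow-up SD, so take an assumed ratio k of follow-up to baseline SD. At 1 year the change variance is k² + 1 − 2ρk and the covariate-adjusted variance is k²(1 − ρ²). The reduction is 37% at k = 0.8, 25% at 0.9, 15% at 1.0, 8% at 1.1 and 3% at 1.2. The two variances differ by (1 − ρk)², so in large samples the covariate form is never the less precise.

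**Deleting the group term under the exchangeable structure.** The weight on baseline becomes the pooled working correlation w = 0.7(2k + k²)/(1 + 2k²), and the 1-year variance is k² + w² − 1.4wk.
- k = 1.1: w = 0.698, variance 0.622 against 0.670, a 7% gain.
- k = 1.2: w = 0.693, variance 0.756 against 0.760, a 0.5% gain.
- k = 1.3: w = 0.686, variance 0.912 against 0.870, a 5% loss.

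**The case against.** The strongest reply is that nothing planned is wrong. The contrast is unbiased, fits the stated aim of assessing change, and was sized on the same basis: 80% power for the two-visit mean is what 177 per group delivers. That stands, and the point is one of efficiency only.

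A reader might infer from the 68% that the 1-year comparison falls short of a promised power. The documents do not support this. They state power for two follow-up points together, none for 1 year alone, and 177 per group is what remains of 489 after the largest drop-out allowed. The documents also give 630 patients, and the Study Timelines counts imply 280 + 244 + 150 = 674. With 27% drop-out those leave about 230 and 246 per group, where unadjusted 1-year power is about 79% and 82%.

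A reader might also take the GEE for the only longitudinal cognitive analysis. It is not: the Missing data section adds random-effects and pattern-mixture models, though without describing any baseline adjustment.

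Three further limits stand. The 15% and 20% are variances; the standard errors move by 8% and 11%. They rest on equal correlations and equal SDs, and scaling Z-scores to the baseline SD does not hold the follow-up SD at 1. And the joint test gains little if the effect appears at one visit only.

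**Conclusion.** The point holds as a loss of precision in a valid analysis. At the plan's correlation, with equal correlations and SDs, the planned model carries a variance of 0.60 where 0.51 is available (1 year) and 0.45 where 0.36 is available (two-visit mean). The direction does not depend on the exact correlation; the size does, as it does on the SD ratio, from a third or more of the variance down to a few per cent.

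It would go too far to call the planned test biased or its sample size wrong. It would also go too far to treat every form of baseline adjustment as free: within the exchangeable GEE, simply removing the group term can cost precision if scores become more variable after surgery.

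**What to change.** In the Aim 1b text, replace the model with one whose outcomes are the two follow-up Z-scores, with baseline Z as a covariate and terms for visit, group, group-by-visit and baseline-by-visit. The last term lets the baseline slope differ between visits.

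An acceptable alternative is a longitudinal model with all three time points, a common baseline mean for the arms and an unstructured covariance. Do not just delete the group main effect while keeping the exchangeable working correlation.

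Use the same form in the supplementary random-effects analysis under Missing data, and state whether the test is the 1-year contrast, the two-visit mean or the joint test, since the gain differs between them.

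The cost is a sentence or two of plan text, settled before unblinding so that the choice cannot look data-driven. It needs no extra patients, visits or measurements, and the 177 per group can stay as a conservative figure under the same assumptions.

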As an additional set of analyses for the multivariable logistic regression models, we will look whether there are interactions (e.g., effect modification) between gender or extra- and intra-cranial arterial stenosis on the composite neurologic outcome. In considering patient sex, we are particular interested in whether or not the effectiveness of the intervention applies equally to women as well as men. Similarly, we are interested in determining whether the association between the intervention and the neurologic end point differs in the presence or absence of clinically significant narrowing in the arteries of the neck and head. In considering the modifying effect of carotid arterial stenosis, we will dichotomize this variable with the cut point of <70% versus  $\geq 70\%$  narrowing based on the NASCET criteria, using the methods for measurement described in **Magnetic Resonance Imaging**. For intracranial arterial stenosis, we will dichotomize the stenosis as  $\geq 50\%$  or <50%. As a second step, we will also consider three categories of arterial stenosis (<50%, 50%–70%, and >70%), which considers the clinically important stenosis definition as defined by the Warfarin-Aspirin Symptomatic Intracranial Disease criteria. Interaction terms for both the binary definition of stenosis and the three categories of stenosis will be incorporated into the regression model, and any statistically significant effect modifications will be determined via standard Wald tests. Finally, we will also consider arterial stenosis in the multivariable logistic regression model as a continuous variable if the inter-rater reliability is high for this variable. Considering arterial stenosis as a continuous variable will allow us to consider possible thresholds of risk for the neurologic end point as a function of a continuous measure of stenosis. We will look for inflection points in the risk of stenosis on the outcome by incorporating linear (e.g., broken arrow regression) and cubic spline terms in the model. If the inter-rater reliability for the continuous measures of stenosis is low, we will consider only the above categories of mild, moderate, and severe stenosis in the regression models.

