Sample size calculations are based on detecting differences in the proportion of patients with an adverse neurologic outcome (DWI lesion, stroke, or cognitive decline 4 to 6 weeks after surgery) between the Control and Intervention groups. We expect that approximately 45% of subjects in the Control Group will experience an adverse neurologic outcome after surgery based on the preliminary data analysis of outcomes of 176 patients. In comparison, we expect that the proportion of the Intervention Group that experiences adverse neurologic outcomes will be reduced by 40-45% (e.g. The frequency of neurologic adverse events will be between 25% and 27%). This magnitude of reduction in the frequency of the composite outcome is within the range that is considered to be clinically important effect (20% to 45% reduction from control frequency) based on prior trials that have evaluated temperature manipulations, pH management, transfusion triggers, and pharmacologic strategies for improving neurologic complications of cardiac surgery . Postoperative MRI is not always feasible for reasons already discussed. According to our calculations, we will need to obtain MRI data on a total of 122 patients in each study arm (244 patients in total) to have 80% power to detect 40% reduction in the composite outcome of stroke, DWI lesion, or cognitive decline 4 to 6 weeks after surgery, assuming that 45% of Control Group patients experience adverse neurologic events. The Type I error is 5%.

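### The Wald test planned for the stenosis interactions fails when an arm-by-stratum cell has no events, which is most likely when the Aim 1a hypothesis is true

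*Combined protocol and SAP*

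**What the plan says.** Study Statistics handles effect modification in two places.

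- **Aim 1/1a, relative-risk analysis.** Unadjusted relative risks are stratified by each modifier, and the plan says: "We will use a test of homogeneity to compare stratum-specific estimates of RR". A Poisson model with robust standard errors is then used to "report stratum-specific adjusted estimates of RR by introducing appropriate interaction terms of these variables and study group in the GLM model".
- **Additional logistic analyses.** Carotid stenosis is split at 70% and intracranial stenosis at 50%. Three categories follow (below 50%, 50–70%, above 70%). For the interaction terms, "any statistically significant effect modifications will be determined via standard Wald tests". A continuous stenosis analysis with splines is added if inter-rater reliability is high.

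Under Objectives, the Aim 1a hypothesis is that the intervention lowers the risk of brain injury in patients with extracranial and/or intracranial stenosis. The Aim 3 text says the effect-modification results will help to weigh benefit and risk in patients with intracranial narrowing.

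Neither Study Statistics nor the later Statistical Analysis Plan section gives an expected stenosis prevalence, a minimum stratum size, a rule for empty cells, or an alternative to the Wald test.

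**The concern.** A Wald test divides the estimate by its standard error. If one arm of a stenosis stratum has no events, the logistic interaction estimate runs to infinity and its standard error grows faster, so the p-value goes to 1 regardless of the evidence. No events among treated stenosis patients is the result that would most favour the Aim 1a hypothesis, so the named test loses its power just when the hypothesis is most true.

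The same table also damages the relative-risk analysis. The robust-Poisson fit returns a stratum relative risk near zero with a small, finite standard error, which looks like overwhelming evidence. With no rule fixed in advance, an analyst who meets an empty cell could report either extreme or choose another test after seeing the data.

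**Working it through.** **Inputs from the documents.** The primary comparison is described as follows: "This will be done using a two-sided test of proportions at 5% significance level". The sample size is set "to have 80% power to detect 40% reduction in the composite outcome", "assuming that 45% of Control Group patients experience adverse neurologic events". The risks are therefore 0.45 and 0.45 × 0.6 = 0.27, with 122 evaluable patients per arm. Stenosis is measured by MRA at the brain MRI visit, so about 122 per arm will have both stenosis data and the complete composite.

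**The plan's own figure.** The pooled two-proportion formula gives

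n = [1.960√(2 × 0.36 × 0.64) + 0.842√(0.45 × 0.55 + 0.27 × 0.73)]² / 0.18² = 110.4.

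With the continuity correction, (110.4/4)[1 + √(1 + 4/(110.4 × 0.18))]² = 121.3, so 122 per arm. The figure is reproduced.

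**Assumed stratum size.** 5%, 10%, 15% and 20% of 122 is about 6, 12, 18 and 24 patients per arm.

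**Step 1: what an empty cell does.** Take stenosis patients at 5/8 (control) v 0/8 (intervention) and the others at 51/114 v 31/114.

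- *Logistic Wald.* SE² = Σ[1/e + 1/(n − e)] over the four cells, which is infinite at e = 0. Software stops at an arbitrary large estimate with an enormous standard error; p = 0.999.
- *Robust Poisson.* A cell with events contributes 1/e − 1/n to SE². The empty cell contributes only 1/n. SE² = (1/51 − 1/114) + (1/31 − 1/114) + (1/5 − 1/8) + 1/8 = 0.234, so SE = 0.48. The log estimate has no finite limit, and software stops near −20 (−20.5 in a similar table with 3/6 v 0/6). The p-value is effectively 0.
- *Likelihood ratio:* p = 0.017. *Firth penalised-likelihood ratio:* p = 0.059.

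**Step 2: the failure needs an exact zero.** Change 0/8 to 1/8. The logistic contrast is −1.683 with SE 1.325, p = 0.20. The robust-Poisson contrast is −1.112 with SE 0.992, p = 0.26. Likelihood ratio gives 0.17 and Firth 0.24. The tests now agree.

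**Step 3: chance of no events in the treated stratum.** With m patients it is (1 − p)^m.

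| m per arm | p = 0.27 (no effect modification) | p = 0.05 (assumed strong benefit) |
|---|---|---|
| 6 | 15% | 74% |
| 12 | 2% | 54% |
| 18 | 0.3% | 40% |
| 24 | 0.1% | 29% |

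**Step 4: power.** Simulated trials of 122 per arm, with risks of 45% v 27% outside the stratum and an assumed 60% v 5% inside it, at two-sided 5%:

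| m per arm | Logistic Wald | Firth |
|---|---|---|
| 6 | about 0% | about 18% |
| 12 | about 12% | about 51% |
| 18 | about 30% | about 74% |
| 24 | about 51% | about 80% |

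Repeated runs differ by up to about 4 percentage points, which does not affect the comparison.

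**Step 5: false positives.** With 45% v 27% in both strata, the robust-Poisson interaction p-value rejects in about 18% of trials at 6 per arm and near 5% from 12 per arm. Logistic Wald rejects in about 1% at 6 and 3% at 12. Firth rejects in 3–5%. A plain likelihood-ratio test rejects in about 7–8% at 6 per arm.

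**The case against.** The strongest case against the point has five parts.

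1. *Stratum size is unknown.* A reader might infer that the stenosis strata will hold only a handful of patients. The documents do not support that. They give no prevalence at these cut points, and enrolment by a neurologic risk score that counts carotid bruit and prior stroke favours diseased patients. The Aim 1a hypothesis also pools extracranial and intracranial disease, a group at least as large as carotid stenosis of 70% or more alone. This stands, so the sizes above are assumptions over a range. With no effect modification the problem has almost gone by 15% prevalence. Under the hypothesised benefit it has not: an empty treated cell still has a 29% chance at 24 per arm.
2. *Two rival tests.* A reader might infer that the plan sets two decision rules that would return p near 1 and p near 0. It does not. The Wald rule belongs to the logistic models. The named test in the relative-risk analysis is homogeneity, in an unspecified form, and the Poisson interaction terms serve to report stratum relative risks. This stands. What remains is the failed logistic test and a misleading reported relative risk.
3. *Gender.* Gender interactions fall under the same analyses, but nothing suggests a sparse gender stratum. The point does not extend to them.
4. *The Firth test is not significant either* in the 5/8 v 0/8 table (0.059). True, but 0.059 reflects the data, whereas 0.999 follows from the empty cell alone.
5. *Limited stakes.* These are secondary analyses, a continuous stenosis analysis may also be run, and a huge standard error is easy to notice. All fair. Noticing it after unblinding still leaves the remedy to be chosen with the result in view.

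**Conclusion.** The point holds in a conditional form. The plan names a test for the stenosis interactions that cannot detect effect modification when a cell is empty, and it has no rule for that case. Under the assumed 60% v 5% effect, the Wald test gives up about 18 to 44 percentage points of power against the Firth test over 6 to 24 patients per arm (18 − 0, 51 − 12, 74 − 30 and 80 − 51). That rests on three assumptions that the documents neither give nor exclude: stratum prevalence of 5–20%, a strong benefit in the stratum, and equal stratum sizes in the two arms.

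The stronger claim that the robust-Poisson model generally produces false subgroup findings is not supported. The excess is about 18% at 6 per arm and is gone by about 12. The primary test of proportions and the 122 per arm are untouched. This is a cheap improvement to a secondary analysis that addresses a named hypothesis.

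**What to change.** - **Logistic analyses (Study Statistics).** For the stenosis interaction terms, binary and three-category, replace the Wald tests with Firth penalised-likelihood ratio tests and profile penalised-likelihood intervals, at all stratum sizes. Applying them throughout avoids a switch that depends on the data. A plain likelihood-ratio test is an acceptable alternative, slightly liberal in the smallest strata.
- **Relative-risk analysis (Aim 1a).** State that where an arm-by-stratum cell has no events, the counts and an exact interval for the risk difference are reported in place of a robust-Poisson relative risk. State also that the robust-Poisson interaction p-value is not used as evidence of effect modification.

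The cost is two or three sentences and standard software, with no new data and no change to the sample size. The Firth test is slightly conservative in very small strata and loses almost nothing when cells are well filled.

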## **OBJECTIVES:**

The specific aims of this proposal are:

**Aim 1:** To determine whether targeting blood pressure to a level above an individual's lower CBF autoregulatory threshold during CPB (cardiopulmonary bypass) reduces the frequency of the composite end-point of clinical stroke, or a diffusion-weighted MRI brain lesion, or postoperative cognitive decline 4 to 6 weeks after surgery, compared with patients who receive standard empiric blood pressure management. **Hypothesis:** Targeting mean arterial pressure during CPB to a level above an individual's lower autoregulatory threshold reduces the risk for brain injury in patients undergoing cardiac surgery.

**Aim 1a:** To assess whether extracranial and/or intracranial arterial stenosis (detected by MR angiography), or other patient characteristics such as age, gender, hypertension, diabetes, or prior stroke, modify the effect of maintaining blood pressure above an individual's lower CBF autoregulatory threshold on the risk for the above composite neurological outcome. **Hypothesis:** Targeting blood pressure during CPB to a level above an individual's lower autoregulatory threshold reduces the risk for brain injury in patients undergoing cardiac surgery who have extra- and/or intra-cranial arterial stenosis.

**Aim 1b:** To assess whether targeting MAP to a level above an individual's lower CBF autoregulatory threshold during CPB reduces the frequency of cognitive decline 1 year after surgery compared with the use of standard blood pressure management.

**Aim 2:** To compare three methods of continuous monitoring of CBF autoregulation derived from the linear regression correlation between cerebral oximetry O2 saturation and blood pressure (oximetry index), near infrared-derived relative total hemoglobin and blood pressure (hemoglobin volume index), and transcranial Doppler measured CBF velocity and blood pressure (mean velocity index). **Hypothesis:** Mean velocity index, cerebral oximetry index, and hemoglobin volume index provide complimentary data on detecting the lower limit of CBF autoregulation.

Aim 2 has been satisfactorily addressed and will no longer be an aim of this project.

**Aim 3:** To evaluate whether perioperative transcranial Doppler measurements of major cerebral artery blood flow velocity can identify patients prone to the composite neurological end-point. **Hypothesis:** Perioperative transcranial Doppler examination can

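### Aim 1a runs about ten interaction tests with none named as decisive: if each is run at 5%, the chance of at least one nominally significant result when no interaction exists is about 28–35%

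*Combined protocol and SAP*

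**What the plan says.** The Aim 1a hypothesis in the Objectives is about one modifier: targeting blood pressure "reduces the risk for brain injury in patients undergoing cardiac surgery who have extra- and/or intra-cranial arterial stenosis". The analysis is wider.

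- **Relative-risk analysis (Study Statistics, Aim 1 to 1b paragraph).** The relevant text begins "To assess potential effect modification by cerebral arterial stenosis, age, gender, hypertension, diabetes, or prior stroke (Aim 1a", and the method is this: "We will use a test of homogeneity to compare stratum-specific estimates of RR". Interaction terms in the Poisson model follow. No significance level is given for these tests. The only level in the paragraph belongs to the Aim 1 comparison: "This will be done using a two-sided test of proportions at 5% significance level".
- **Logistic analysis (Study Statistics, the paragraph on interactions with gender and stenosis).** Gender and stenosis are examined again. Carotid stenosis is split at 70% and intracranial stenosis at 50%, and three categories follow as a second step. Interactions are fitted for the two-level and the three-level codings alike. The rule for judging them is that "any statistically significant effect modifications will be determined via standard Wald tests".
- **Continuous stenosis (same paragraph).** If inter-rater reliability is high, stenosis also enters as a continuous variable with broken-line and spline terms: "We will look for inflection points in the risk of stenosis on the outcome".

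The Study Statistics, Missing data and Statistical Analysis Plan sections contain no multiplicity adjustment for Aim 1a, no statement of which interaction decides it, and no exploratory label for it. The Aim 3 text says the effect-modification results will help weigh benefit and risk in patients with narrowed intracranial arteries.

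**The concern.** The plan intends to act on these results but does not say which one answers the question. A chance interaction among many tests could be reported as benefit confined to patients with stenosis, or as absence of benefit in women. For stenosis itself, three codings can give three answers, and the stated rule would accept any significant one. If the coding is chosen after the results are seen, the choice cannot be defended.

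**Working it through.** **Inputs from the plan.** Control event rate 45%; 40% relative reduction, so 27% under the intervention; 122 per arm (244 in total); 80% power; two-sided 5% for Aim 1. Six modifiers. Three stenosis codings with stated interaction terms, plus gender again, on the logistic scale.

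**Assumptions (not in the plan).** Each interaction test is run at 5%. In the main six-modifier runs: age split at the median, 30% women, hypertension 80%, diabetes 45%, prior stroke 15%, carotid stenosis of at least 70% in 10% or 20%, intracranial stenosis of at least 50% in 15% or 30%, and latent correlation between modifiers 0 or 0.3.

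**1. The plan's sample size.** With mean rate 0.36 and difference 0.18:

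n = [1.96 × √(2 × 0.36 × 0.64) + 0.842 × √(0.45 × 0.55 + 0.27 × 0.73)]² / 0.18² = 110.4, so 111 per arm.

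With continuity correction: (110.4 / 4) × [1 + √(1 + 4 / (110.4 × 0.18))]² = 121.3, so 122 per arm. This matches the plan and fixes the setting for what follows. The plan states no error rate for Aim 1a that could be reproduced.

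**2. Chance of at least one significant interaction when none exists.** For k independent tests at 5% it is 1 − 0.95^k. The simulated column uses 244 patients and no interaction.

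| Family | Independent tests | Simulated |
|---|---|---|
| Six modifiers, relative-risk homogeneity tests | 1 − 0.95^6 = 26.5% | 21–25% |
| Three stenosis codings, logistic Wald tests | 1 − 0.95^3 = 14.3% | 10–13% |
| Six modifiers + three codings + gender again (ten tests) | 1 − 0.95^10 = 40.1% | 28–32% |

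- The six-modifier runs covered both the planned effect (45% v 27%) and no effect (45% v 45%), with 1,200 trials per setting. The Monte Carlo standard error is √(0.25 × 0.75 / 1200), about 1.3 percentage points. Raising the correlation between modifiers to 0.5 under the planned effect gives 20–21%.
- The 10–13% for stenosis rests on an assumed 30% of patients with at least 50% stenosis and 15% with at least 70%. With 20% and 8% it falls to 8–9%.
- Another ten-test family, with a continuous stenosis interaction in place of the second gender test, gave 29–35%. That is the source of the upper end of 28–35%. Without that term the range is 28–32%.
- The simulated values lie below the independent ones because the tests overlap and because some tests with small strata reject in fewer than 5% of null trials.

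**3. How well a real interaction would be seen.** Suppose 30% of patients have stenosis, with relative risk 0.6 in them and 1.0 in the rest. There are then 36.6 and 85.4 patients per arm in the two strata. The variance of the difference in log relative risk is

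0.55 / (36.6 × 0.45) + 0.73 / (36.6 × 0.27) + 2 × 0.55 / (85.4 × 0.45) = 0.136, so SE = 0.369.

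Then |ln 0.6| / SE = 0.511 / 0.369 = 1.39, and power is Φ(1.39 − 1.96), about 28% (27% by simulation). With power this low, one nominally significant interaction among ten is weak evidence.

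**The case against.** The best defence is that the plan is more ordered than a bare count of tests suggests. The only stated Aim 1a hypothesis concerns stenosis. The logistic models are introduced as secondary, and their interaction terms as additional. Binary codings come first, categories second, and a continuous form last and only if reliable. The plan uses homogeneity and interaction tests rather than comparing p-values within subgroups, which is sound practice. The Wald sentence concerns the stenosis codings; the six-modifier paragraph gives no threshold and speaks of reporting estimates.

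All of this is correct, and it narrows the point. It does not remove it: an order of presentation does not say which result decides Aim 1a, and the one decision rule that is written accepts any significant coding.

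Three stronger readings are tempting, and the documents do not support them:

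- A reader might count the continuous, spline and inflection-point analyses as further interaction tests. The text gives interaction terms only to the binary and three-category codings. It describes the continuous work as a search for thresholds in the risk of the outcome, and makes it conditional on reliability.
- A reader might take Aim 1a as confirmatory because it stands under the primary outcome heading. All the aims stand there, and the plan says its secondary outcomes are included in that part.
- A reader might equate these rates with the rate of false subgroup claims. They are chances of a nominally significant test. A false claim follows only if the result is reported as a finding.

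**Conclusion.** The concern holds in limited form. Aim 1a has about ten interaction tests, no designated decisive one, no adjustment and no exploratory label. At an assumed 5% per test and 244 patients, the chance of at least one nominally significant interaction when none exists is about 21–25% for the six modifiers, about 10–13% for the stenosis codings, and about 28–35% for the whole family. The prevalences and correlations behind these figures are assumptions; the plan gives none. The plan's list of modifiers is introduced with examples, so six is a minimum. The primary Aim 1 comparison keeps its 5% error, so the trial's main conclusion is not at risk. This is a cheap improvement.

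**What to change.** In the two Study Statistics paragraphs on effect modification:

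1. Name one test for Aim 1a: the treatment-by-stenosis interaction in the Poisson relative-risk model, at two-sided 5%, with stenosis defined once from the plan's own cut-points as carotid at least 70% or intracranial at least 50%.
2. Label age, gender, hypertension, diabetes, prior stroke and every other stenosis coding as exploratory. Report interaction relative risks with 95% confidence intervals and declare no significance.
3. State that the conclusion on the stenosis hypothesis in the Objectives rests on the interaction estimate, not on the result within the stenosis subgroup.
4. Make the change before unblinded analysis.

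The cost is wording only: no new patients, data or procedures. The small downside is that the other subgroup results cannot be presented as confirmed. That includes sex, in which the plan declares particular interest. Naming one test does not add power, so a non-significant stenosis interaction should be read through its confidence interval and not as evidence of equal effect.
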